In summary, anodal tDCS targeting M1 will be selected since this approach influences sensational components of pain perception. BreESTim is shown to modulate the affective component of pain perception. Therefore, we expect that that combined BreESTim and tDCS treatment has addictive analgesic effects as compared to BreESTim or tDCS alone. We will test this treatment in healthy subjects and for neuropathic pain management in common patient populations, such as brain injury (BI), spinal cord injury (SCI), and amputation.

4. Description of Study:

This study has 4 experiments. The main idea is to test the effectiveness of the new intervention for neuropathic pain management for healthy subjects and one patient population (SCI, BI, or amputation) in each experiment. We request to recruit 20 subjects (5 subjects each group for healthy, SCI, BI and amputation). Overall, We plan to adopt recently published BreESTim (Li et al. 2013) and tDCS(Boggio et al. 2008) research protocols in this experiment. Briefly, this will be a single-center, randomized, cross-over trial to determine whether there is additive analgesic effect of a single session of combined and BreESTim and tDCS stimulation in healthy, and other patient subjects.

[figure not shown]
Subject recruitment

A total of 20 patients is planned to be enrolled as a pilot study for the following patient populations: healthy, BI, SCI and amputation. The estimated number of total patients will be calculated based on our pilot study with 5 subjects for each group. Patient subjects will be screened at the outpatient clinic of TIRR Memorial Hermann Hospital. Subjects will be recruited and enrolled in the project if they meet the inclusion and exclusion criteria (see subject population).

The interventions/Experimental procedures

The experiment consists of 3 sessions, including 1) BreESTim + Sham tDCS (i.e., BreESTim only), 2) BreESTim +active tDCS, and 3) tDCS only. Three sessions will be conducted on three different days with an interval of at least 24 hours. In each session, a conditioning tDCS (active or sham) will be performed first, then followed by BreESTim.

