Pre-intervention and post-intervention measurements include electrical sensation and pain thresholds and warm sensation and heat pain thresholds as used in our recent study (Li et al. 2013). In addition, visual analogue scores (VAS), modified visual analogue scores (mVAS) will be recorded in patient subjects. These measurements will be taken pre- and post-intervention for both sessions. VAS has been extensively used and validated (McCarthy et al. 2005). mVAS further quantifies the effect of pain reduction by measuring duration and amount of change in VAS, i.e., how much pain was reduced and how long it lasted (reduction × hours). It is necessary to note that pain rating is very subjective. This cross-over design uses subjects as their own control.

Heart rate variability as objective outcome measurements

We have been searching for non-invasive objective pain outcome assessment. Heart rate variability has recently recognized a physiological marker for pain assessment (Cowen et al. 2015), see also Appelhans & Leucken 2008 (both articles are uploaded to the iRIS).

We propose to add 5 minutes of Heart Rate recordings before and after the interventions. Experimental procedures and data analysis will be adopted from the above articles.

Two-way repeated measures ANOVA with factors INTERVENTIONS (3 levels, BreESTim only, tDCS only and tDCS+BreESTim) and TIME (pre- and post-intervention) will be used determined statistical significance for each threshold (electrical sensation and pain thresholds, and thermal sensation and pain threshold, mVAS). It is expected that BreESTim + tDCS will have better analgesic effect than BreESTim or tDCS alone.

7. Potential Risks/Discomforts:

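### mVAS has one value per session but is assigned to a pre/post ANOVA, VAS is assigned to no test, and only an omnibus test is planned for a two-comparison hypothesis

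*Combined protocol and SAP*

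**What the plan says.** All the analysis text is in section 6, Data Analysis.

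- **Pain scores.** "In addition, visual analogue scores (VAS), modified visual analogue scores (mVAS) will be recorded in patient subjects". They therefore concern Experiments 2 to 4 (3 × 5 = 15 patients), not the healthy subjects.
- **Timing.** "These measurements will be taken pre- and post-intervention for both sessions". Section 4 gives three sessions, so the word for two is a slip.
- **Definition of mVAS.** "mVAS further quantifies the effect of pain reduction by measuring duration and amount of change in VAS", explained as "how much pain was reduced and how long it lasted", with the formula reduction × hours.
- **Test.** A two-way repeated measures ANOVA with INTERVENTIONS (BreESTim only, tDCS only, both) and TIME (pre, post) is to be used "for each threshold (electrical sensation and pain thresholds, and thermal sensation and pain threshold, mVAS"). VAS is not in the list. No other test for it appears in the text reviewed. Part of the background before section 4 was not available, but an analysis rule for VAS would not be expected there.
- **Hypothesis.** "It is expected that BreESTim + tDCS will have better analgesic effect than BreESTim or tDCS alone". The summary just before section 4 says the same: "combined BreESTim and tDCS treatment has addictive analgesic effects as compared to BreESTim or tDCS alone" (read as additive).
- **Later use.** Section 4, under subject recruitment: "The estimated number of total patients will be calculated based on our pilot study with 5 subjects for each group".

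**The concern.** The two pain scores seem to have changed places. The score built from a pre-to-post change is put into a model that needs separate pre and post values. The score that has those values is left out. For mVAS, an analyst would have to invent a baseline or drop a factor. For VAS, the direct pain rating in the three patient experiments, the analyst would have no planned analysis and would choose one after seeing the data.

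The second issue is separate. The hypothesis makes two directed comparisons: combination against BreESTim, and combination against tDCS. A three-level ANOVA effect says only that the interventions are not all alike. A significant result could be read as support for the combination when the data show something else. This applies to the thresholds as much as to the pain scores.

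**Working it through.** The plan states no alpha, power, SD or effect size, so it has no figure to reproduce.

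**1. What values does mVAS have?** Reduction × hours needs a pre VAS, a post VAS and the time the reduction lasted. It is defined only after an intervention, so there is one value per subject and session. Call it y.

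**2. Planned ANOVA with post values only.** TIME has a single level. TIME and INTERVENTIONS × TIME then have 0 degrees of freedom and no F statistic. On illustrative data with 5 subjects, only INTERVENTIONS could be computed: F(2,8) = 5.109, p = 0.037.

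**3. Planned ANOVA with every pre value set to 0.**
- INTERVENTIONS works on the session mean, (0 + y)/2 = y/2.
- INTERVENTIONS × TIME works on the session change, y − 0 = y.
- A one-way repeated measures ANOVA on the post values works on y.

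F does not change when the data are multiplied by a constant, so the three tests are identical for any data. The illustrative data agree:

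| Subjects | INTERVENTIONS | Interaction | One-way on post values |
|---|---|---|---|
| 5 | F(2,8) = 5.109, p = 0.037 | same | same |
| 15 | F(2,28) = 3.923, p = 0.031 | same | same |

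TIME compares the subjects' mean y with 0. It asks whether mean mVAS differs from zero and does not compare interventions.

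**4. VAS.** With pre and post values in three sessions it fills the 3 × 2 layout. For one group of 5, the interaction has (3 − 1) = 2 and (3 − 1)(5 − 1) = 8 degrees of freedom.

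**5. Omnibus test against the hypothesis.** For a pre/post outcome, the interaction F equals the one-way repeated measures F on the change scores. Assumptions, none from the plan: one group of 5 analysed alone, normal change scores with SD 1, equal correlation ρ between sessions, two-sided 5%.

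Take a case in which the hypothesis is false: the combination equals BreESTim and both are 1 SD better than tDCS. The means are 1, 1, 0, with average 2/3, and the squared deviations sum to 1/9 + 1/9 + 4/9 = 2/3.

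Noncentrality λ = n × (2/3) / (1 − ρ) = 3.333 / (1 − ρ). The critical value of F(2,8) is 4.459.

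| ρ | λ | Omnibus rejects |
|---|---|---|
| 0 | 3.33 | 25.5% |
| 0.5 | 6.67 | 46.5% |
| 0.8 | 16.67 | 85.7% |

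If instead the combination equals tDCS and both are 1 SD worse than BreESTim, the deviations are the same size, so λ and the rejection rates are the same. In the first case the true contrast of combination against BreESTim is 0, and its paired t test would favour the combination in only 2.5% of trials.

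**6. Precision of a contrast at n = 5.** The 95% half-width, with the SD of the difference at its assumed value, is t(0.975, 4) × √(2(1 − ρ)/5) = 2.776 × √(2(1 − ρ)/5). This gives 1.76, 1.24 and 0.79 SD at ρ = 0, 0.5 and 0.8.

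**The case against.** The timing sentence nominally covers mVAS, and zero is the only baseline its definition allows. On that reading the ANOVA runs, gives the correct between-intervention F, and makes TIME a meaningful question of whether pain fell at all. This stands in part: the comparison of interventions survives. But the plan does not state the zero, and one of the three tests then merely duplicates another.

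Omitting VAS may be deliberate, since mVAS is built from it, and weighting by duration is what such a score is for. That is a fair defence of mVAS as an outcome. It does not replace a VAS analysis, because the product cannot be taken apart: 1 point for 6 hours and 6 points for 1 hour both score 6. Adding VAS does add a correlated test to five listed outcomes with no stated multiplicity control.

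The omnibus issue is indeed separate from the mVAS mismatch, applies to every outcome, and its rates rest wholly on assumed values.

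Some stronger readings are tempting but unsupported:

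- **Later sample size compromised.** Section 4 says later numbers will come from the pilot but not from which outcome.
- **False positives from TIME when pain worsens.** This depends on how worsening is scored. The plan gives no rule, so no error rate can be attached to it.
- **Both contrasts must be significant.** The plan sets no such rule, and at 5 subjects it would have little power: about 9%, 22% and 60% at ρ = 0, 0.5 and 0.8 if the combination is 1 SD better than each single treatment.

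**Conclusion.** The concern holds, at minor severity. Steps 1 to 4 follow from the plan's own definition and need no assumed values. As listed, mVAS does not fit the TIME factor, and VAS, which does, has no test. The omnibus rates of 25.5%, 46.5% and 85.7% illustrate the separate issue under the assumptions in step 5. They are not properties of this trial, for which no SD, correlation or effect is given.

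A reader might infer that the mVAS comparison between interventions or the threshold ANOVAs are invalid. They are not. The mVAS comparison is the same valid one-way test with or without a zero baseline, and the thresholds have true pre and post values. What the thresholds share is the gap between an omnibus test and a two-comparison hypothesis.

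**What to change.** Amend section 6:

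1. Compare the single mVAS value per session across the three interventions within subject, without TIME. With 5 subjects the one-way repeated measures F has 2 and 8 degrees of freedom.
2. Add VAS to the outcomes in the pre/post ANOVA.
3. For every outcome, thresholds included, report two within-subject contrasts with confidence intervals: combination against BreESTim only, and combination against tDCS only. Use the pre-to-post change for VAS and the thresholds, and the session value for mVAS. Describe the ANOVA as an omnibus test only.

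Do not require both contrasts to be significant in a pilot with 5 per group. The estimates and intervals are the useful output.

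The cost is a few sentences, with no added subjects, visits or measurements, since VAS is already recorded. The downsides are one more correlated outcome (six in place of five) and wide intervals, about ±0.8 to ±1.8 SD under the assumptions in step 6.

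### For the thresholds and mVAS, the planned 3 x 2 ANOVA names no deciding term and no contrast, so a significant F would not show that the combination beats the better of its two components

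*Combined protocol and SAP*

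**What the plan says.** Section 4 (Description of Study) gives the aim of the randomized cross-over as "to determine whether there is additive analgesic effect of a single session of combined and BreESTim and tDCS stimulation". The summary just before it expects that "combined BreESTim and tDCS treatment has addictive analgesic effects as compared to BreESTim or tDCS alone" (evidently meaning additive). The sessions are set out as follows: "The experiment consists of 3 sessions, including 1) BreESTim + Sham tDCS (i.e., BreESTim only), 2) BreESTim +active tDCS, and 3) tDCS only". Each of the four populations contributes 5 subjects.

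Section 6 gives the test: "Two-way repeated measures ANOVA with factors INTERVENTIONS (3 levels, BreESTim only, tDCS only and tDCS+BreESTim) and TIME (pre- and post-intervention) will be used". It is applied to five outcomes, the wording being "determined statistical significance for each threshold (electrical sensation and pain thresholds, and thermal sensation and pain threshold, mVAS". The next sentence is "It is expected that BreESTim + tDCS will have better analgesic effect than BreESTim or tDCS alone". On mVAS, Section 6 says "mVAS further quantifies the effect of pain reduction by measuring duration and amount of change in VAS", and defines it as the reduction multiplied by the hours it lasted.

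Heart rate variability is left to cited articles and is outside this point. The supplied text gives no alpha, SD, effect size, post hoc test or success rule.

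**The concern.** The question has two directional parts: is the combination better than BreESTim with sham tDCS, and is it better than tDCS only? The stated test has three F ratios for each outcome (INTERVENTIONS, TIME and their interaction), and nothing says which one answers it.

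- TIME asks whether outcomes change on average over the three sessions. It says nothing about differences between sessions.
- The interaction asks whether the three changes differ in any way. It can be significant because tDCS alone is weaker, with the combination no better than BreESTim.
- mVAS has no natural pre-intervention value, yet it is listed for a model with a pre/post factor.
- Every session contains active treatment, while the aim is worded as an additive effect.

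At stake is the pilot's conclusion. A significant F with the combination on top could be reported as evidence that tDCS adds to BreESTim when it does not.

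**Working it through.** **Inputs.** From Sections 4 to 6: n = 5 per experiment, 3 sessions, 2 times. There is no planned power figure to reproduce. Assumed: two-sided 5% tests; change of subject i in session j = b_i + μ_j + e_ij, with independent e_ij of SD 1 (the unit below). The subject effect b_i cancels from the interaction and from the contrasts.

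**1. Interaction F.** With two times, this is the one-way repeated measures F on the changes, with 2 and 2(n−1) = 8 df and critical value 4.46. The noncentrality is λ = n Σ(μ_j − μ̄)².

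Suppose the combination equals BreESTim and both exceed tDCS by δ. The deviations from the mean are δ/3, δ/3 and −2δ/3, so λ = 5 × (2/3)δ².

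| δ | λ | F significant | F significant and combination first | Both paired contrasts (4 df) | Both pooled contrasts (8 df) |
|---|---|---|---|---|---|
| 1 | 3.33 | 25% | 13% | 1.4% | 2.1% |
| 1.5 | 7.5 | 51% | 26% | 1.9% | 2.4% |
| 2 | 13.3 | 77% | 38% | 2.3% | 2.5% |

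The F column is from the noncentral F; simulation (at least one million experiments per row) agrees and gives the other columns. As a check, the combination and BreESTim are exchangeable here, so the combination should rank first in about half of the significant results: 25.5/2, 51.3/2 and 76.9/2 give 12.7, 25.7 and 38.5%.

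λ is the same when the combination truly exceeds both components by δ (deviations 2δ/3, −δ/3, −δ/3). The F test therefore has the same chance of significance whether the combination beats both components or only tDCS.

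**2. TIME F.** This is the square of a one-sample t (4 df) on each subject's mean change, whose SD is √(1/3 + σ_b²). If all three sessions produce the same change of 0.5/1/1.5 SD:
- σ_b = 0: significant in 32/82/99%. At 1 SD the noncentrality is √5/√(1/3) = 3.87.
- σ_b = 1: significant in 12/32/59%. At 1 SD it is √5/√(4/3) = 1.94.

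The interaction stays at 5% throughout.

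**3. mVAS.** Set the pre value to 0, the only obvious choice. Each session mean is then mVAS/2 and each change is mVAS. The INTERVENTIONS F and the interaction F use the same numbers up to a factor of 2, so they are identical. One simulated data set gave 2.3465 on 2 and 8 df for both.

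**4. Additivity.** Let u be the change without active treatment, taken as common to the sessions, and let τ_C, τ_B and τ_T be the effects of combination, BreESTim and tDCS. The expected changes are C = u + τ_C, B = u + τ_B and T = u + τ_T. Then C − B = τ_C − τ_B, which is free of u. But C − B − T = (τ_C − τ_B − τ_T) − u, which measures departure from additivity only if u = 0.

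**5. What the two contrasts can deliver at n = 5.** The standard error of a difference is √(2/5) = 0.632. The 95% half-width is 2.776 × 0.632 = 1.76 SD with separate paired errors (4 df), or 2.306 × 0.632 = 1.46 SD with the interaction error term (8 df, sphericity assumed).

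| True advantage over both components | F significant | Both pooled | Both paired |
|---|---|---|---|
| 1 SD | 25% | 16.5% | 9% |
| 1.5 SD | 51% | 41% | 25% |
| 2 SD | 77% | 69% | 49% |

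**The case against.** The strongest reply is that this is a declared pilot with 5 subjects per population, that the expected direction is written down, and that any competent analyst would follow a significant F with session comparisons. Much of this stands. The direction is stated, and the misreading needs a reader who stops at F. It does not close the gap: an expectation does not say which comparisons are made, whether both must succeed, or which ANOVA term they come from, and Section 6 does intend to determine statistical significance for each outcome.

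A second reply is that the supplied text omits a part before Section 4, and that Section 4 adopts published protocols that cannot be seen here. The claim of absence is therefore limited to the supplied text.

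Four stronger readings are tempting but not supported:

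- A reader might infer a false-positive rate of 13 to 38%. The plan does not say that a significant F counts as success, so these are not error rates of a stated rule.
- A reader might infer that a combination ranked last could be declared the winner because F has no direction. The stated direction and the session means would expose this: on the same assumptions, F is significant with a truly worst combination ranked first in almost no experiments.
- A reader might infer that the mVAS comparison is biased. It is not; the layout is mis-specified, but the session comparison survives in it.
- A reader might infer that the later study will be sized on the wrong quantity. Section 4 says only "The estimated number of total patients will be calculated based on our pilot study with 5 subjects for each group" and does not name the estimate.

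It is also too strong to say that additivity cannot be assessed at all. It can be if untreated change is taken as zero, and Section 4 and the summary before it may intend no more than better than each alone.

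**Conclusion.** The point holds for the thresholds and mVAS, and should be fixed. In the supplied text, the only stated test has no deciding term and no contrast, and neither the TIME F nor the interaction F can by itself show that the combination beats its better component. That conclusion is logical and needs no assumed effect size.

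Its size does rest on assumptions: n = 5, two-sided 5%, and independent, equal-variance session changes. On these, the room for misreading is about 13/26/38%, against roughly 1 to 2.5% when both directional contrasts are required. The consequence is for interpretation and reporting; the data to be collected are unaffected. The mVAS and additivity points are smaller: a factor that does not apply, and a word that needs an unstated assumption.

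**What to change.** Change the wording of Section 6:

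1. For each threshold, base the comparison on the pre-to-post change (INTERVENTIONS x TIME).
2. Prespecify two contrasts, combination minus BreESTim with sham tDCS and combination minus tDCS only, each with a 95% confidence interval.
3. Choose the error term in advance: the interaction error (8 df) if sphericity is accepted, otherwise separate paired errors (4 df).
4. Claim superiority to each component only if both intervals exclude zero in favour of the combination.
5. Compare mVAS across the three sessions without TIME.
6. Word the conclusion as superior to each component alone, not as additive.

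No new data, visits or subjects are needed. The cost is a stricter rule. At a true advantage of 1/1.5/2 SD over both components it succeeds in about 16.5/41/69% of experiments with the pooled error, or 9/25/49% with paired errors, where F would be significant in 25/51/77%. With half-widths of 1.46 or 1.76 SD, the estimates and intervals should carry the interpretation of this pilot, not the significance verdict.
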